### Sponsor Signatures

Signature: [REDACTED] Date: [REDACTED]

Sponsor

Signature: [REDACTED] Date: [REDACTED]

Sponsor

Signature: [REDACTED] Date: [REDACTED]

Sponsor

Signature: [REDACTED] Date: [REDACTED]

Study Director (CRO)

Signature: [REDACTED] Date: [REDACTED]

Statistician (CRO)

		CLINICAL STUDY PROTOCOL SYNOPSIS SirTex Medical Study Number: STX2301
Study Title	Study to Calculate the Radiation-Absorbed Dose of Technetium-99m Macroaggregated Albumin (99mTc-MAA) to the Whole Body and Non-Liver Critical Organs (MAapping Study)	
Identifying Regulatory Numbers	Clinicaltrials.gov – NCT05848947	
Study Objective	To evaluate the dosimetry of 99mTc-MAA after intra-arterial administration to the whole body and non-liver critical organs.	
Product Description	Technetium-99m macroaggregated-albumin consists of macroaggregated-albumin particles labeled with technetium-99m (99mTc), with a size between 10 and 90 microns in diameter. 99mTc is a gamma emitting radioactive isotope commonly used for diagnostic localization studies.	
Study Design	The investigation is a prospective, single center, open label, single-arm study. Patients enrolled in the study will have 3 imaging scans taken after 99mTc-MAA injection, the final of which will occur between 18 and 24 hours post-injection.	
Number of Sites & Subjects	The study will be conducted at one clinical site in the United States and will enroll 5 subjects.	
Study Population	The intended population for the study is patients who are undergoing evaluation for SIR-Spheres administration. All subjects enrolled will already be planned to receive 99mTc-MAA per clinical standard of care, and the decision to offer enrollment in the study will occur only after the decision to deliver 99mTc-MAA for SIRT planning has already been made.	
Endpoints	

1. Mean absorbed dose (Gy) for the whole body

2. Mean absorbed dose (Gy) for critical non-liver organs

3. Mean activity (Bq) for the whole body

4. Mean activity (Bq) for critical non-liver organs

5. Effective dose (Gy) for the whole body

	
Study Eligibility Criteria	
Subjects must meet all the following inclusion criteria:
 

1. Willing, able, and mentally competent to provide written informed consent

2. Age 18 or older at the time of consent

3. Patients who are being evaluated for SIR-Spheres treatment eligibility

 
Subjects must not meet any of the following exclusion criteria:
 

1. Patients who are contraindicated for SIR-Spheres treatment

2. Patients who are contraindicated for 99mTc-MAA per the manufacturer's package insert

	

		CLINICAL STUDY PROTOCOL SYNOPSIS Sirtex Medical Study Number: STX2301
Study Duration	Enrollment is expected to take approximately 2 months. Each study subject will actively participate in the study through 24-hour follow-up. The overall study duration, from screening the first patient to the final follow-up visit, data analysis, and final report, is expected to be approximately 3 months.	
Study Sponsora	Sirtex Medical Inc. [name] [name]	
Study Site	Inland Imaging [name] [name]	
Contract Research Organization (CRO)	BRIGHT Research Partners [name] [name] [REDACTED] [REDACTED]	

a Detailed contact information is maintained in a separate Sponsor Contact List managed by the CRO

## 1.0 ABBREVIATIONS

The following is a list of abbreviations used in the body of this document. Abbreviations solely used in tables (e.g., table headers) are described in the table footer and are not included below.

Abbreviation	Description
99mTc	Technetium 99m
99mTc-MAA	Technetium 99m-labeled macroaggregated albumin
ADL	Activities of daily living
AE	Adverse event
Bq	Becquerel
CFR	Code of federal regulations (U.S.)
(e)CRF	(electronic) case report form
CRO	Contract research organization
CT	Computed tomography
CTCAE	Common terminology criteria for adverse events
EDC	Electronic data capture database
FAS	Full analysis set
FDA	Food and Drug Administration (U.S.)
FUDR	Floxuridine
GCP	Good clinical practice
Gy	Gray
HCC	Hepatocellular carcinoma
HIPAA	Health Insurance Portability and Accountability Act
ICF	Informed consent form
ICH	International Conference on Harmonisation
IND	Investigational New Drug
IRB	Institutional Review Board
ISO	International Organization for Standardization
ITT	Intent to treat
keV	Kilo electron-volt
LEAP	Low-energy all purpose
LEHR	Low-energy high resolution
MAA	Macroaggregated albumin
MIRD	Medical Internal Radiation Dose
mSv	Millisievert
NDA	New Drug Application
NMI	Nuclear medicine imaging
OLINDA	Organ Level INternal Dose Assessment
PET	Positron emission tomography

Abbreviation	Description
PI	Principal investigator
ROI	Region of Interest
SAE	Serious adverse event
SIR-Spheres	SIR-Spheres® Y-90 resin microspheres
SIRT	Selective internal radiation therapy
SPECT	Single photon emission computed tomography
VOI	Volume of interest
Y-90	Yttrium-90

## 2.0 CLINICAL BACKGROUND

The selective internal radiation therapy (SIRT) technique, developed by Gray in the 1980s and 1990s, delivers microspheres containing yttrium-90 (Y-90), a high-energy beta-emitting isotope with no primary gamma emission, directly into the vasculature of hepatic tumors. The goal is to deliver lethal doses of radiation to tumors but sublethal doses to surrounding healthy tissue.

Prior to administration of Y-90 microspheres, an evaluation of arterial flow at the implantation site is made using Technetium Tc 99m-labeled macroaggregated albumin (99mTc-MAA); this is often referred to as a “lung shunt” study or mapping procedure. After intra-arterial administration of 99mTc-MAA, the patient is imaged via planar, single photon emission computed tomography (SPECT), or SPECT/CT. The patient-specific image is analyzed and used in calculating the patient-specific radiation dose for implant per the microsphere instructions for use.

SIR-Spheres® Y-90 resin microspheres (SIR-Spheres) were approved by the Food and Drug Administration (FDA) as a Class III medical device in 2002 for the treatment of unresectable metastatic liver tumors from primary colorectal cancer with adjuvant intrahepatic artery chemotherapy of floxuridine (FUDR). TheraSphere™ Y-90 glass microspheres (Boston Scientific) were approved by the FDA as a Class III medical device in 2021 for the treatment of patients with hepatocellular carcinoma (HCC). At present, the DOORwaY90 study (IDE G200352) is evaluating use of SIR-Spheres Y-90 for the treatment of HCC.

While commonly used for mapping procedures prior to SIRT, 99mTc-MAA is labeled for intravascular administration but not intra-arterial administration. The purpose of this study is to fulfill an FDA request for a dosimetry study to evaluate the radiation-absorbed dose of 99mTc-MAA to the whole body and non-liver critical organs. Study data will support radiation risks described in SIR-Spheres Y-90 product labeling.

## 3.0 REGULATORY CLASSIFICATION

This clinical investigation of a marketed drug is exempt from the Investigational New Drug (IND) requirements as all of the criteria for an exemption in § 312.2(b) are met:

Requirement for exemption	Comments
The drug product is lawfully marketed in the United States.	99m Tc-MAA is lawfully marketed in the United States. 99m Tc-MAA is part of the current clinical standard of care for preparation of SIRT procedures and has been in commercial use since 1976.
The investigation is not intended to be reported to FDA as a well-controlled study in support of a new indication and there is no intent to use it to support any other significant change in the labeling of the drug.	The investigation will not support a new indication or change in labeling for 99m Tc-MAA.

Requirement for exemption	Comments
In the case of a prescription drug, the investigation is not intended to support a significant change in the advertising for the drug.	The investigation is not intended to change advertising for 99mTc-MAA.
The investigation does not involve a route of administration, dose, patient population, or other factor that significantly increases the risk (or decreases the acceptability of the risk) associated with the use of the drug product (21 CFR 312.2(b)(1)(iii)).	
The risk associated with the use of 99mTc-MAA will not be significantly increased nor will the acceptability of risk be decreased due to the low levels of radiation to be absorbed by non-target organs as well as low-level whole-body exposure, all of which are expected to be < 15mGy (Kappadath). This level of exposure is similar to that seen when MAA is delivered for pulmonary imaging in standard practice according to its labeling.
 
Current standard practice for radioembolization treatment planning makes use of nuclear medicine imaging (NMI) of 99mTc-MAA arterial distributions for the assessment of lung shunting and extrahepatic uptake; 99mTc-MAA will be administered under the operation of an authorized user per 10 CFR 35.290 as stated in the study protocol. Subjects in the investigation are already intended to receive 99mTc-MAA for SIRT planning regardless of their enrollment, and thus the study does not involve the use of 99mTc-MAA or any other drug apart from their already intended treatment (Gates).
 
In this context, the use of 99mTc-MAA is associated with improved quality of subsequent SIRT procedures, thus reducing the overall risk to the subject.
 
As noted above, all subjects enrolled in the study would already be receiving MAA as SIRT candidates; hence, the only study-specific procedure is SPECT-CT, which will be performed for MAA dosimetry. The radiation exposure from diagnostic CT procedures is estimated to be in the range of 1 to 10 mSv, with an abdominal CT effective dose of 8 mSv (McCollough). In assessing the associated risk, McCollough et al. conclude that there is no convincing epidemiological evidence of increased cancer incidence or mortality at doses less than 100 mSv.

The investigation is conducted in compliance with the requirements for review by an IRB (21 CFR part 56) and with the requirements for informed consent (21 CFR part 50).	The investigation will be conducted in compliance with the requirements for review by an IRB (21 CFR part 56) and with the requirements for informed consent (21 CFR part 50), as stated in the study protocol.

Requirement for exemption	Comments
The investigation is conducted in compliance with the requirements of §312.7 (i.e., the investigation is not intended to promote or commercialize the drug product).	
The investigation will be conducted in compliance with the requirements of §312.7, as the investigation is not intended to promote or commercialize 99mTc-MAA with updated labeling.
 

• The objective of the investigation is solely to address an FDA request to evaluate the dosimetry of 99mTc-MAA in the context of preparation for SIRT procedures.

• The sponsor of the investigation has no financial or other interest in 99mTc-MAA or in its promotion or commercialization.

 
The use of 99mTc-MAA in this context is part of the current clinical standard of care for preparation for SIRT procedures.

## 4.0 99mTc MAA DESCRIPTION

99mTc-MAA is lawfully marketed in the United States. Product labeling is provided with the commercial dose of 99mTc-MAA. The macroaggregated albumin (MAA) particles are used to simulate the distribution of the therapeutic SIR-Spheres resin microspheres prior to administration of the therapy. MAA is obtained by heat denaturation of stannous chloride treated human serum albumin under controlled conditions. MAA is provided to the radiopharmacy as 10- or 15-mL (depending on the manufacturer) vials containing white lyophilized powder. Upon radiolabeling with sodium pertechnetate 99mTc injection solution, the stannous reduced 99mTc binds to the aggregated albumin. The kits do not contain any bacteriostatic agents; however, the rubber septum should be cleaned with alcohol swabs or bacteriostatic agents following the removal of the plastic cap.

Volume of the vials, maximum 99mTc activity, amounts of MAA, human serum albumin, total tin (as  $\text{SnCl}_2 \cdot 2\text{H}_2\text{O}$ ), stannous chloride, sodium chloride and pH adjustment agents may vary depending on the manufacturer.

[figure not shown]
Typically, individual syringes of 3-5 mCi of 99mTc-MAA are provided by the radiopharmacy to client sites to be used in the mapping procedure.

99mTc decays by isomeric transition with a physical half-life of 6.02 hours. The principal photon that is useful for gamma SPECT imaging is present with an abundance of 89.07% and energy of 140.5 keV.

### 4.1 Principle of Operation / Mechanism

During SIRT, radioactive Y-90 microspheres are intra-arterially infused proximal to the tumor target to provide direct irradiation of tissue and destruction of the microvascular bed (Figure 1).

**Figure 1. SIR-Spheres Selectively Delivered to Liver Tumor**

During the mapping procedure in preparation for SIRT,  $^{99m}\text{Tc-MAA}$  is administered intra-arterially from the intended SIRT treatment location. The infused MAA particles aggregate in the microvasculature of the tumor and liver tissue. The patient is imaged using SPECT/CT imaging to count the gamma emission from the  $^{99m}\text{Tc}$ . This serves as a simulated therapeutic procedure that provides information for the treating physician in order to optimize dosimetric predictions for the therapy and minimize potential for over administration of activity/dose to non-targeted areas.

## 5.0 OBJECTIVE

To evaluate the dosimetry of  $^{99m}\text{Tc-MAA}$  after intra-arterial administration to the whole body and non-liver critical organs.

## 6.0 ENDPOINTS

### 6.1 Primary Endpoints

The primary endpoints for this study are as follows:

1. Mean absorbed dose (Gy) for the whole body
2. Mean absorbed dose (Gy) for critical non-liver organs
3. Mean activity (Bq) for the whole body
4. Mean activity (Bq) for critical non-liver organs
5. Effective dose (Gy) for the whole body

### 6.2 Rationale for Study Endpoints

The study endpoints are selected to provide an assessment of radiation activity and dose over time, with primary interest in dose to critical non-liver organs and the whole body. The endpoints will therefore provide useful information in understanding the behavior of  $^{99m}\text{Tc-MAA}$  in patients undergoing planning for a subsequent SIRT procedure.

## 7.0 STUDY DESIGN

### 7.1 Overall Design

The investigation is a prospective, single center, open label, single-arm study. Patients enrolled in the study will have 3 imaging scans taken after 99mTc-MAA injection, the final of which will occur between 18 and 24 hours post-injection.

### 7.2 Number of Sites & Subjects

The study will be conducted at one clinical site in the United States and will enroll 5 subjects.

### 7.3 Study Population

The intended population for the study is patients who are undergoing 99mTc-MAA injection as evaluation for subsequent SIRT. All subjects enrolled will already be planned to receive 99mTc-MAA per clinical standard of care, and the decision to offer enrollment in the study will occur only after the decision to deliver 99mTc-MAA for SIRT planning has already been made.

### 7.4 Study Duration

Enrollment is expected to take approximately 2 months. Each study subject will actively participate in the study through 24-hour follow-up. The overall study duration, from screening the first patient to the final follow-up visit, data analysis, and final report, is expected to be approximately 3 months.

### 7.5 Subject Eligibility Criteria

#### 7.5.1 Inclusion Criteria

Subjects must meet all the following inclusion criteria:

1. Willing, able, and mentally competent to provide written informed consent
2. Age 18 or older at the time of consent
3. Patients who are being evaluated for SIR-Spheres treatment eligibility

#### 7.5.2 Exclusion Criteria

Subjects must not meet the following exclusion criteria:

[figure not shown]
1. Patients who are contraindicated for SIR-Spheres treatment
2. Patients who are contraindicated for 99mTc-MAA per the manufacturer's package insert

## 8.0 STUDY METHODOLOGY

Study assessments and data collection points are visually represented in **Figure 1** and **Table 1** and are described below. Study procedures should be followed as they have been designed to address any known or foreseeable factors that may compromise the outcome of the clinical study or the interpretation of results (e.g., subject baseline characteristics, concomitant

medication, the use of medical devices, and subject-related factors such as age, gender, or lifestyle) and methods for addressing these factors (e.g., subject selection, statistical analysis).

**Figure 1: Study Flow Diagram**

**Table 1: Schedule of Study Activities**

Assessment	Study Visit				
	Screening	Procedure	0-2 hours	6-10 hours	18-24 hours
Eligibility criteria	X				
Informed consent	X				
Demographics/medical history	X				
99mTc-MAA infusion		X			
Imaging (SPECT/CT) 			X	X	X
Adverse event assessment		X	X	X	X

Used for quantitative analyses

## 8.1 Screening Visit

The study team will screen patients for the study. Screening is defined as the process of reviewing a patient's medical records against the study eligibility (inclusion and exclusion) criteria to determine if the patient is potentially eligible to enroll in the study. It is expected that the medical records will contain adequate information to determine if a patient meets most of these criteria. If the investigator (or designee) determines the patient meets standard of care inclusion and exclusion criteria, they can be consented for study participation; informed consent may be obtained prior to or at the time of the procedure.

### 8.1.1 Informed Consent Process

Prior to enrolling patients in this study, the site will be required to have an Institutional Review Board (IRB) approved informed consent form (ICF). To ensure compliance with informed consent requirements, the contract research organization (CRO) must review any modifications made to the sponsor's template ICF prior to IRB submission.

Written informed consent will be obtained from the patient prior to the subject's participation in the study. The investigator (or authorized designee) will explain the nature of the planned treatment and objectives of the study to the patient, along with any costs to the subject and payments for participation. The investigator will allow adequate time for the patient to read and review the consent form and to ask questions. When the investigator has reasonable assurance that the patient has an acceptable level of comprehension and the patient voluntarily agrees to participate, the patient and the investigator (or authorized designee) will sign and date the ICF.

The site will retain the original signed ICF in the subject's study records and will provide a copy of the ICF to the subject. The site will document the consent process (e.g., that the subject was consented, the date on which the consent was obtained, that a copy of the signed ICF was given to the subject, and that no study procedures were conducted prior to obtaining consent) in the subject's medical records.

Subjects will be informed of any new information that may make him/her change their mind about staying in the study. Subjects may be asked to sign a new ICF if this occurs.

### **8.1.2 Vulnerable Population**

To preserve the ethical integrity of this study, the sponsor does not intend to enroll vulnerable subject populations (e.g., incarcerated persons or adults with severe cognitive challenges) in this study since such populations may be coerced or compelled to participate in a clinical study without a full understanding or against their will these subjects should be excluded (in consideration of 21 CFR 56.111(b)).

## **8.2 Point of Enrollment & Numbering of Study Subjects**

A patient will be considered enrolled as a study subject when the investigator deploys any release of the 99mTc-MAA into the patient. The lowest available subject number will be assigned, progressing sequentially for each enrolled subject thereafter.

### **8.3 Procedure Visit**

The intra-hepatic 99mTc-MAA infusion and scan will be conducted by a trained interventional radiologist; steps are briefly outlined below.

- Establish the anticipated treatment volume using angiography assessed by imaging (e.g., cone beam CT)
- Select the hepatic artery with a microcatheter corresponding to the anatomical area of interest, and in a position that will simulate treatment with SIR-Spheres Y-90 resin microspheres
- Attach a syringe containing 150 MBq of 99mTc-MAA and infuse it into the hepatic artery via the microcatheter
- Flush and remove the microcatheter
- Transfer the patient to nuclear medicine for SPECT/CT imaging within 2 hours

An adverse event (AE) assessment will be performed and the results will be recorded on the AE case report form (CRF).

### **8.4 Subject Follow-Up (3 timepoints: 0-2 hours, 6-10 hours & 18-24 hours)**

Subjects will be evaluated at the three specified imaging timepoints post- 99mTc-MAA injection. The assessments described below will be performed at each timepoint, and results will be recorded on the relevant eCRFs.

- SPECT/CT in accordance with the acquisition protocol as described in **Section 8.4.1**
- Adverse event assessment

At the conclusion of this follow-up subjects will exit from this study via completion of the Study Completion CRF. Subjects will continue to be followed by their physician per usual care.

#### 8.4.1 SPECT/CT Acquisition Protocol

The SPECT/CT acquisition protocol outlined below ensures quantitative imaging. To determine the image calibration factor (i.e., cps/MBq), a cylindrical phantom (Jaszczak phantom), will be filled with a uniform distribution of 99mTc (target activity of 400 MBq). The filling volume will be determined by weighing (i.e., difference between filled and empty phantom).

The reconstructed cylindrical phantom data will be used to determine a setup-specific image calibration factor for 99mTc:  $ICF = \frac{C}{T \cdot A_{Calibrator}}$  where C is the counts in the reconstructed image within a cylindrical volume of interest (VOI) corresponding to 130% of the radius and 120% of the height of the phantom, T is the acquisition duration (unit: s), and ACalibrator (unit: Bq) is the activity dispensed

CT Parameters	Good quality low noise (e.g., 130 kV, 30 mAs)
SPECT Acquisition Parameters	360 scan range, 120 projections, 20 to 30 seconds per stop
Collimator	LEAP or LEHR
Primary Energy Window	126-154 keV (e.g., 140 ± 10%)
Scatter Energy Window	98-126 keV (e.g., 112 ± 12.5%)
Reconstructions	OSEM3D with 2 iterations, 16 subsets
Corrections	AC + SC + RR (optional)
Field of View	Entire liver, entire lungs, superior bowel
Transverse Image Array Size	128 x 128

Abbreviations: kiloelectronvolt (keV), low-energy all purpose (LEAP), low-energy high resolution (LEHR), milliampere-seconds (mAs)

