#### 8.4.2 Imaging Analysis

Quantitative gamma SPECT/CT will be performed over the chest and abdomen of the patient at specified timepoints after intra-arterial administration of 99mTc-MAA. Absorbed dose in units of mGy/GBq for each organ of interest and total absorbed dose within the imaged area will be calculated using a 510(k) cleared software product. Mean absorbed doses ± standard deviation for each region of interest will be calculated for the study population.

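### Does Section 8.4.1 bias the measured activities upward by giving no reference time for the phantom activity?

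*Combined protocol and SAP*

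**What the plan says.** Section 8.4.1 sets out how reconstructed counts become activity. A Jaszczak phantom is filled uniformly with 99mTc ("target activity of 400 MBq"), and its volume is found by weight: "The filling volume will be determined by weighing (i.e., difference between filled and empty phantom". The calibration factor is ICF = C/(T × A_Calibrator). C is the counts in a cylindrical volume somewhat larger than the phantom, T is the scan duration in seconds, and A_Calibrator is given by "unit: Bq) is the activity dispensed". The factor's unit is introduced with the words "To determine the image calibration factor (i.e., cps/MBq". The parameter table that follows lists the corrections as "AC + SC + RR (optional".

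Section 8.4 has each subject scanned three times, "SPECT/CT in accordance with the acquisition protocol as described in" Section 8.4.1. Section 8.4.2 says absorbed doses are "calculated using a 510(k) cleared software product" and does not describe that product's calibration or decay handling. Section 4.0 states that 99mTc "decays by isomeric transition with a physical half-life of 6.02 hours".

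**The concern.** Read literally, the formula takes the activity as dispensed and the counts as scanned. T covers only the length of the scan, so it does not account for time between assay and scan. Filling the phantom takes some time, and with a half-life near six hours even a modest delay matters. If the dispensed value went in undecayed, A_Calibrator would be too large, ICF too small, and any activity obtained as count rate divided by ICF too large.

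Such an error would be shared by every scan using that factor. It would not average out over the five subjects of Section 7.2, and the standard deviation would not reveal it. It would enter the activity endpoints of Section 6.1 (in Bq) directly, and the dose endpoints wherever dose is computed from ICF-derived activity. Section 2.0 says the data will support the radiation risks described in the product labeling, so accurate absolute quantification is the purpose of the study.

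The unit label looks like a second defect: the factor is called cps/MBq while A_Calibrator is in Bq.

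**Working it through.** The plan states no calibration error, delay or reference time, so there is no figure of its own to reproduce. The check is of direction and size.

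**Inputs.** Half-life 6.02 h (Section 4.0); phantom target 400 MBq, 120 projections and 20 to 30 s per stop (Section 8.4.1). The delay from assay to phantom scan is not in the documents; 0.25 to 2 h is assumed.

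**Effect of delay.** The decay constant is λ = ln 2/6.02 = 0.1151 per h. After delay t the remaining fraction is f = exp(−λt). With an undecayed A_Calibrator, ICF is multiplied by f and derived activity by 1/f, so the overstatement is 1/f − 1 = 2^(t/6.02) − 1.

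| Assumed delay | f | Overstatement |
|---|---|---|
| 0.25 h | 0.9716 | +2.9% |
| 0.5 h | 0.9441 | +5.9% |
| 1 h | 0.8912 | +12.2% |
| 2 h | 0.7943 | +25.9% |

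At 1 h, 400 × 0.8912 = 356.5 MBq remains in the phantom. Conversely, an error b needs a delay of ln(1 + b)/λ: 10.3 min for 2%, 25.4 min for 5% and 49.7 min for 10%.

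**Decay during the scan.** The scan lasts 120 × 20 s = 40 min to 120 × 30 s = 60 min if each projection is its own stop, or 20 to 30 min with two detector heads (an assumption). The mean count rate relative to the start is (1 − e^(−λT))/(λT), with T here in hours: 0.981 at 20 min, 0.972 at 30, 0.963 at 40 and 0.945 at 60. If phantom and patient scans both fall in the same range, the worst mismatch is a ratio of 1.0096 (20 v 30 min) or 1.0191 (40 v 60 min), in either direction. This is small, and it vanishes when the durations match.

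**Units.** Counts/(s × Bq) is cps/Bq, which differs from cps/MBq by a factor of 10^6. Carried through by mistake, it would turn the 150 MBq infusion of Section 8.3 into 150 million MBq. Nobody would miss that, so it is a labelling slip and not a source of bias.

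**What the 12.2% requires.** Three things must hold together: the reading is entered undecayed, the delay is 1 h, and the software does not correct for decay. The documents establish none of them. Weighing does not supply the delay: it serves the filling volume, which is not in the ICF formula, and the text does not say that it precedes the scan. The corrections row does not settle the second or third condition either. It lists image corrections alongside the reconstruction settings, whereas decaying a dose-calibrator reading to scan time is done on the reading.

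**The case for a change.** The strongest case for a change is that absolute activity is a primary endpoint and the text as available omits the one item that fixes its scale. A shared calibration error would go undetected in a descriptive, single-arm summary. Under half an hour of delay is enough for 5%. The remedy costs one sentence and uses times already recorded by the dose calibrator and scanner. Stating where decay is applied would also guard against correcting twice.

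The arithmetic and the direction stand, and no other section supplies a reference time. The step from an unstated reference time to an uncorrected one does not stand. Decaying the assay to scan time is basic to any 99mTc calibration, and a site set up for quantitative SPECT will do it whether or not the protocol says so. The definition also breaks off without a full stop just before the table, exactly where a reference time would have been written, so the plan cannot safely be said to lack one.

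The reach into dose is uncertain too. If the software scales image counts to the known administered activity, ICF cancels and the dose endpoints are untouched. If the error did occur, it would overstate exposure and not hide it. The worry that a factor might be applied to scans made with another collimator or resolution-recovery setting is already met, because Section 8.4.1 describes the factor as specific to the setup.

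**Conclusion.** The concern does not call for a change. It describes a routine step that is not spelled out in the available text, and competent imaging staff would fill the gap the same way: take the net phantom activity, decay it once to the start of the phantom scan, and use units that match cps/MBq. If that step were skipped and the software did not make up for it, ICF-derived activities would be overstated by 2^(t/6.02) − 1, or 2.9% to 25.9% for assumed delays of 0.25 to 2 h. That range rests on assumed delays and an assumed omission, not on anything the plan states. The dose endpoints would follow only if they are computed from those activities. The unit mismatch is clerical. A query to the site confirming the reference time and single decay correction would be reasonable housekeeping, but neither the design nor the analysis depends on an amendment.

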### **9.3 Analysis of Primary Endpoints**

The primary endpoints are defined in **Section 6.1** and will be presented descriptively under the general principles cited above. Summary statistics for each endpoint will be reported at each of the three timepoints at which they are measured, thereby obtaining activity (GBq) and dose (Gy) over time related to 99mTc-MAA as part of SIRT planning. As the study is nonrandomized, summary statistics of primary interest are those for the enrolled population as a whole and

evaluation of subgroups is not planned *a priori* and no hypothesis testing against predefined null hypotheses or between subgroups is expected.

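### Whole-body dose and whole-body activity are primary endpoints, but the plan images chest and abdomen, totals dose only within that area and gives no conversion; effective dose has no stated calculation and the wrong unit

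*Combined protocol and SAP*

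**What the plan says.** Section 6.1 lists five primary endpoints. Three concern the whole body: endpoint 1, "Mean absorbed dose (Gy) for the whole body"; endpoint 3, "Mean activity (Bq) for the whole body"; and endpoint 5, "Effective dose (Gy) for the whole body". The objective in Section 5.0 also names the whole body.

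Section 8.4.1 sets the field of view as "Entire liver, entire lungs, superior bowel". Section 8.4.2 says that "Quantitative gamma SPECT/CT will be performed over the chest and abdomen of the patient". It promises "Absorbed dose in units of mGy/GBq for each organ of interest", and for a total it says only that "total absorbed dose within the imaged area will be calculated using a 510(k) cleared software product". The software is not named.

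Table 1 schedules these SPECT/CT scans at three timepoints. It lists no whole-body scan and no excreta or blood counting. Section 9.3 adds only descriptive statistics: "Summary statistics for each endpoint will be reported at each of the three timepoints at which they are measured".

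MIRD and OLINDA are in the abbreviation list (Section 1.0) but are not used in the body. Section 13.1.2 names a Statistical Analysis Plan among the study-specific plans, but no derivation from it appears in the text.

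**The concern.** For endpoints 1 and 3, the one total that the plan defines is a different quantity from the endpoint. A team that follows Sections 8.4.1, 8.4.2 and 9.3 to the letter obtains regional figures. It must then either leave the two endpoints unreported or report a chest-abdomen figure under a whole-body name. Endpoint 5 has a different problem: effective dose is normally built from organ doses, and the plan states no model, no weighting and no organ list for it.

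Section 2.0 says that the study answers an FDA request covering the whole body and that its data will support the radiation risks in SIR-Spheres labeling. With five subjects and no stated method, the conversion could be chosen after the data are seen. One input, net administered activity, cannot be recovered later if the syringe and its residual are not assayed on the day.

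**Working it through.** The plan gives no whole-body figure to reproduce, and there is no hypothesis test or sample-size calculation behind this point. The check sets endpoints against measurements and then uses simple arithmetic.

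**1. Endpoint against measurement**

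- Endpoint 1, whole-body dose: the plan computes total dose in the imaged area. No conversion is stated.
- Endpoint 3, whole-body activity: the plan images chest and abdomen. No whole-body measurement or model is stated.
- Endpoint 5, effective dose: no calculation is stated. The unit is Gy, while Section 3.0 quotes an abdominal CT effective dose of 8 mSv.

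**2. Are imaged-area and whole-body values interchangeable?** Let f be the share of activity outside the field and m the share of body mass imaged. Neither is in the documents, so both are assumed here. Counting only energy absorbed where it is emitted, a simplification that ignores photons crossing the field boundary:

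- activity, imaged / whole body = 1 − f
- mean dose, imaged area / whole body = (1 − f) / m

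With f = 0, the activity ratio is 1, but the dose ratio is 1/0.6 = 1.67 at m = 60% and 1/0.4 = 2.5 at m = 40%. With f = 30%, the activity ratio is 0.70 and the dose ratio runs from 0.70/0.6 = 1.17 to 0.70/0.4 = 1.75. The dose ratio equals 1 only when 1 − f happens to equal m. These values show that the quantities differ; they do not estimate an error in this study.

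**3. Dose needs a time integral.** Absorbed dose accumulates, so it needs activity integrated over time, including after the last scan. Inputs: 150 MBq (Section 8.3), half-life 6.02 h (Section 4.0), physical decay only.

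- Total: 150 × 6.02 / ln 2 = 1302.8 MBq·h.
- Share after a last scan at time t: 2^(−t/6.02), which is 12.6% at 18 h and 6.3% at 24 h.

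The tail is not negligible, so its rule should be stated. A separate dose at each of three timepoints, as Section 9.3 reads, is not a natural form for endpoints 1 and 5.

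**4. What a remainder-of-body term can and cannot do.** Taking the remainder as administered minus in-field activity closes the balance, but the remainder then absorbs any SPECT calibration error. Section 8.4.1 uses a setup-specific calibration factor from a phantom, at one site, so that error may be common to all subjects. As an assumed example, take a true remainder of 5% and a shared 5% over-read: in-field activity reads 0.95 × 1.05 = 99.75%, so the remainder reads 0.25% in every subject. Averaging five subjects would not remove this. Excreted activity, if any, would also be counted in the remainder under a no-excretion assumption, which tends to overstate retained activity.

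**The case against.** The strongest reply is that little may be missed. Section 4.1 says the particles lodge in tumor and liver tissue, and Section 3.0 describes the imaging as assessing lung shunt and uptake outside the liver. The field covers those sites. Endpoint activity in Bq comes from the phantom calibration, the software may offer a whole-body model, and a separate Statistical Analysis Plan may hold the derivation. The study is descriptive, with five subjects.

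Most of this stands, and it limits the point. A reader might infer that three of the five endpoints are mis-measured or cannot be obtained. The documents do not support that: organ-level modelling could supply all three without another scan, and effective dose lacks a method rather than a measurement. A reader might also infer a definite error in whole-body dose, but the out-of-field share is not given. Nor does the typical 3–5 mCi syringe in Section 4.0 establish an error: 150 MBq is 150/37 = 4.05 mCi, inside that range, and nothing says the typical range is this study's spread.

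The reply does not supply the conversion. High in-field coverage does not make a regional mean dose a whole-body mean dose. Listing MIRD and OLINDA as abbreviations states no method; PET and ITT are also listed there and not used.

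**Conclusion.** The concern holds as a mismatch for endpoints 1 and 3 and as a missing calculation with a wrong unit for endpoint 5. It rests on the absence of any conversion in the available text; a derivation in a separate Statistical Analysis Plan would answer most of it once cited. No size of error is claimed, and the 1.17 to 2.5 dose ratios rest on assumed mass and activity shares. Because the endpoints can still be derived and the study is small and descriptive, this should be fixed, but it does not invalidate the design.

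**What to change.** No extra scan is needed.

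- **Labels.** In Sections 6.1, 8.4.2 and 9.3, call directly imaged totals *chest-abdomen imaged region* and do not report them as whole body. Keep imaged-region activity at each actual scan time as the measured activity endpoint.
- **Administered activity.** In Section 8.3 and the eCRF, record net administered activity for each subject: syringe assay minus residual, with times. The mGy/GBq unit in Section 8.4.2 needs an activity denominator in any case.
- **Whole-body and effective dose.** Integrate activity over time for the liver and each imaged organ from the three scans, with a stated rule for the tail. Add a remainder-of-body source: time-integrated net administered activity (physical decay, no excretion) minus time-integrated in-field activity. Enter these in named organ-level dose software, with the body mass or phantom stated. Report one whole-body dose and one effective dose per subject, not one per timepoint.
- **Limits.** Label these figures, and any whole-body activity figure, as model-based. State that the no-excretion assumption tends to overstate retained activity and that the remainder absorbs calibration error, possibly shared across subjects. List each subject's remainder, including negative values, and give a sensitivity result with the remainder set to zero.
- **Unit.** Give effective dose in mSv.
- **Existing derivation.** If a separate Statistical Analysis Plan already holds the method, cite it in Section 9.3.

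The cost is wording in three sections, two assays per subject (10 for five subjects), one extra source in the software and one sensitivity run. The whole-body results will be model-based.

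The fallback is to restate endpoints 1 and 3 as imaged-region quantities, define or drop endpoint 5, and narrow the objective. It is simpler to do, but the whole-body part of the FDA request described in Section 2.0 is then not met.
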